#### **9.3.1. Baseline Data**

Examples of baseline data captured in ARTIS can be found in [Appendices 1 and 2](#), respectively. The data captured include, but are not restricted to, the following: age, sex, years since diagnosis, disease severity, drug history, comorbidities (eg, history of malignancies), current concomitant medications, history of serious infection, history of opportunistic infection, history of herpes zoster, history of fractures, ever malignancy events (i.e. history of malignancy excluding NMSC, and specifically history of NMSC, history of lymphoma and history of lung cancer), and history of therapeutic procedures.

To facilitate the evaluation of the safety endpoints of MI and MACE, the following CV risk factors will also be evaluated at baseline: age (patients  $\geq 65$  years versus  $< 65$  years) and history of the following conditions: chronic kidney failure, diabetes, hypertension, statin use (as a proxy for history of hypercholesterolemia), previous MI, coronary heart disease, stable

angina pectoris, and history of therapeutic procedures to treat cardiovascular disease (e.g. coronary artery bypass graft (CABG) and percutaneous coronary intervention (PCI)).

To facilitate the evaluation of the primary endpoint of VTE, the following VTE risk factors will be evaluated at baseline and/or, for some risk factors, within specific time periods prior to index date as specified: age, previous VTE, undergoing major surgery from date of hospital admission to one month after date of discharge, MI within previous 3 months prior to index date, heart failure, use of combined hormonal contraceptives or hormone replacement therapy within 3 months of index date, malignancy, diabetes mellitus, hypertension, inpatient care because of RA (i.e., RA as main diagnostic listing; from date of admission to date after discharge).

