 The potential mechanism for increased PML risk is poorly understood. PML will be evaluated using both on drug and once-exposed always at risk approaches.

The primary analysis will assume a once exposed always at risk paradigm, as is frequently used in study of malignancy risk due to bDMARDs. Under this approach, follow up for each cohort continues from the cohort index date until the first of a malignancy event, loss to follow up, death or end of study. Follow up for each exposure cohort continues after switching to a new drug or discontinuation of treatment. This approach maximizes follow up time and the ability to capture long latency events, ie, events that occur or are detected years after exposure. Under this approach, events will be double-counted if a patient indexed to bDMARD switches to tofacitinib and a malignancy occurs subsequent to tofacitinib exposure. That is, the event will be assigned to both the bDMARD and the tofacitinib exposure cohorts as will the corresponding person years since index to the respective cohorts. Because tofacitinib is expected to be used as a later line therapy, switching is expected to be non-random with most tofacitinib patients having been included in the bDMARD cohort prior to initiation of tofacitinib. In such cases, the bDMARD rate will have more associated person-years and thus a relatively lower rate than the corresponding rate in the tofacitinib cohort.

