For these analyses, the exposure cohorts will be analyzed overall, by previous biologics use and monotherapy and combination therapy with concomitant conventional synthetic disease modifying antirheumatic drugs (csDMARDs). Increased risk of malignancy (excluding NMSC), MACE, MI, serious infection, VTE, herpes zoster, PML, and gastrointestinal perforation events, as well as an increase in mortality, in patients treated with a combination therapy with MTX specifically will be described if sample sizes are sufficient, in the interim and final reports. These and potentially other agreed upon strata will be determined a priori and included in SAP filed with Sponsor. The general analytic approach will be descriptive and include rates of events of interest within stratified treatment cohorts. Data will be presented as number of events, crude and age/sex-standardized incidence rates.

Any final comparative report will adjust for differences in severity of disease and other confounders will be completed using appropriate multivariate, propensity score matching, or inverse probability weighting. The final report will also evaluate the rates of safety events of interest within the elderly. The outcomes reported will include hospitalized infections, OI, herpes zoster, fractures, hepatitis, GI perforations, malignancies, CV events, and all-cause mortality, with subgroupings and selected additional outcomes per agreement. HRs from multivariable Cox regressions adjusting for sex, age, year of treatment start, treatment history, disease severity, comorbidities, and other potential confounders to be agreed upon by ARTIS and the Sponsor and defined in an SAP prior to analysis. The final SAP will also specify an ICD-algorithm harmonised with other registers conducting similar analyses for serious infections, CV events, GI perforations, and herpes zoster (HZ).

Any comparative safety reports will leverage data linkages to obtain data on all comorbidities that have led to hospitalization, cancer or death. Data on malformations and perinatal morbidities and mortality can also be obtained from the birth register.

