Status at entry	Exposed Tofacitinib	Third biologic		Second biologic		Comparator Cohorts First biologic			
		TNFi	Non-TNFi	TNFi	Non-TNFi	TNFi	Non-TNFi	Biologics-naive	General population
Total days spent in hosp (median, IQR)									
Reason for discontinuing previous biologic									
Safety, of those with information (%)									
Inefficacy, of those with information (%)									
Other, of those with information (%)									
Missing, of total (%)									

COPD=Chronic obstructive pulmonary disease; DAS: Disease activity scale; DMARD=disease modifying antirheumatic drug; HAQ= health assessment questionnaire; Hx=history IQR=interquartile range; MI=myocardial infarction; N=count; NSAID = non-steroidal anti-inflammatory drug; RA=Rheumatoid Arthritis; TNFi=tumor necrosis factor inhibitor.

090177e199570500\Approved\Approved On: 13-Feb-2022 20:25 (GMT)

Table II. Total number of events, crude and standardized incidence rates							
Outcome	Cohort	Patients	Events	Person-Years	IR	Std IR	Mean follow-up, yrs
For each event of interest							
	Tofacitinib						
	0 previous biologics						
	1 previous biologics						
	2 previous biologics						
	3+ previous biologics						
	Third bio starters, TNFi						
	Third bio starters, non-TNFi						
	Second bio starters, TNFi						
	Second bio starters, non-TNFi						
	First bio starters, TNFi						
	First bio starters, non-TNFi						
	Bonaïve RA Patients						
	General Population						
Notes: IR, Incidence Rate, RA=rheumatoid arthritis; Std IR standardised incidence rate to the age/sex distribution in the tofacitinib cohort; TNFi=tumor necrosis factor inhibitor; yrs=years.							

090177e199570500\Approved\Approved On: 13-Feb-2022 20:25 (GMT)

090177e199570500\Approved\Approved On: 13-Feb-2022 20:25 (GMT)

Table III. Results from adjusted Cox regressions comparing tofacitinib initiators to comparator cohorts for each outcome									
Outcome	Tofacitinib initiators vs.	HRa	95% CI	HRb	95% CI	HRc	95% CI	HRd	95% CI

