
Notes: Analysis was only made for comparisons where both cohort had at least 5 observed events. HR: Hazard Ratio. CI: Confidence Interval.  HRa: stratified for year at start, adjusted for age and sex.  HRb: stratified for year at start, adjusted for age, sex, prior number of days in inpatient care, history of infection, cancer, MI, diabetes, COPD, and joint replacement surgery.  HRc: stratified for year at start, adjusted for age, sex, prior number of days in inpatient care, history of infection, cancer, MI, diabetes, COPD, and joint replacement surgery, Rheumatoid factor, HAQ(linear), RA disease duration, DAS28(linear), DMARDs, steroids. Complete case analysis.  HRd: as HRc but using a missing indicator, and quartiles, for HAQ and DAS28.
									

Table IV. Results from crude and adjusted Cox regressions comparing tofacitinib to biologic DMARDs (bDMARDs), stratified by the number of bDMARDs									
Outcome	Number of previous biologics	HRa	95% CI	HRb	95% CI	HRc	95% CI	HRd	95% CI
Each event	0								
	1								
	2								
	Aggregate estimate								

Notes: Analysis was only made for comparisons where both cohorts had at least 5 observed events. HR: Hazard Ratio. CI: Confidence Interval.  HRa: stratified for year at start, adjusted for age and sex.  HRb: stratified for year at start, adjusted for age, sex, prior number of days in inpatient care, history of infection, cancer, MI, diabetes, COPD, and joint replacement surgery.  HRc: stratified for year at start, adjusted for age, sex, prior number of days in inpatient care, history of infection, cancer, MI, diabetes, COPD, and joint replacement surgery, Rheumatoid factor, HAQ(linear), RA disease duration, DAS28(linear), DMARDs, steroids. Complete case analysis.
									

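### The Appendix 2 Cox models do not match the promised adjustment: no prior-biologic count, no 3+ stratum, and most collected CV and VTE risk factors left out

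*Protocol*

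**What the plan says.** If the comparative analysis proves feasible, Section 9.7.2 of the protocol plans "HRs from multivariable Cox regressions adjusting for sex, age, year of treatment start, treatment history, disease severity, comorbidities" and further confounders to be defined in an SAP. Section 8 makes the same promise. Section 9.7.2 also says that the reports will hold tables in line with the Appendix 2 shells.

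Those shells name four covariate sets:

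- HRa controls for start year (as strata), sex and age only.
- HRb, whose list also ends with joint replacement, reads "HRb: stratified for year at start, adjusted for age, sex, prior number of days in inpatient care, history of infection, cancer, MI, diabetes, COPD".
- To these, HRc adds "Rheumatoid factor, HAQ(linear), RA disease duration, DAS28(linear), DMARDs, steroids. Complete case analysis".
- HRd keeps the HRc covariates and recodes HAQ and DAS28.

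Table IV is headed "Results from crude and adjusted Cox regressions comparing tofacitinib to biologic DMARDs (bDMARDs), stratified by the number of bDMARDs". Its rows are 0, 1, 2 and an aggregate estimate. Table II has a tofacitinib row for "3+ previous biologics", and Table I has the same category. The bDMARD comparators in both tables end at third-biologic starters.

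Section 9.3.1 introduces its cardiovascular list with "To facilitate the evaluation of the safety endpoints of MI and MACE, the following CV risk factors will also be evaluated at baseline", and gives a similar list for VTE. Section 9.7.2 uses these factors to stratify incidence rates (at least one factor versus none). Section 9.3.2 states the expected place of the drug: "Because tofacitinib is expected to be used as a later line therapy".

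**The concern.** Channeling is the main threat that the protocol names. Section 9.9 expects tofacitinib patients to have longer disease, several failed therapies and more comorbidity. The entry criteria may widen the gap: the bDMARD cohort is limited to RA diagnosed after 1 January 2012 (Section 9.2.1.2), while the tofacitinib cohort has no such limit (Section 9.2.1.1). Number of prior biologics is therefore a leading confounder, and it is in none of the four models.

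Table IV does control for line, but only up to two prior biologics. The patients in whom channeling should be strongest have no same-line comparison, and a reader of the aggregate estimate cannot tell whether they are in it.

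MI, MACE and VTE are safety concerns with their own risk-factor lists, yet one covariate list serves every outcome. If the omitted factors differ between cohorts, the hazard ratio for those outcomes is biased, in a direction that cannot be known beforehand.

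**Working it through.** The point contests no stated figure, so the check sets the text side by side. The illustrations in step 4 rest on assumed inputs.

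**1. Treatment history.** HRa: year, age, sex. HRb: adds inpatient days and history of infection, cancer, MI, diabetes, COPD and joint replacement. HRc: adds rheumatoid factor, HAQ, disease duration, DAS28, DMARDs and steroids. HRd: HRc recoded. Prior-biologic count is in 0 of 4. The item DMARDs in HRc is not defined as line of therapy; Table I lists concomitant DMARDs and number of previous biologics as separate variables.

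**2. Line strata.**

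| Prior biologics | Tofacitinib, Tables I and II | bDMARD cohort, Tables I and II | Table IV row |
|---|---|---|---|
| 0 | yes | first biologic | yes |
| 1 | yes | second biologic | yes |
| 2 | yes | third biologic | yes |
| 3+ | yes | none | none |

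Table IV covers 3 of the 4 tofacitinib strata. Nothing says how 3+ patients enter the aggregate.

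**3. Risk factors.** Section 9.3.1 lists 9 CV factors and 10 VTE factors. Age, diabetes, hypertension and MI are on both lists, so 9 + 10 − 4 = 15 are distinct (counting MI history and recent MI as one).

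- In HRb to HRd: age, MI, diabetes, cancer (4).
- Partial proxy: major surgery by joint replacement, inpatient RA care by inpatient days (2).
- Absent: hypertension, chronic kidney failure, statin use, coronary heart disease, stable angina, coronary procedures, previous VTE, heart failure, hormonal therapy (9).

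Table I tabulates four of the nine (hypertension, coronary heart disease, angina, coronary procedures), but no model uses them.

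**4. Illustrations only.**

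*Line left out, no drug effect.* Assume prior-biologic shares (0/1/2/3+) of 10/20/30/40% for tofacitinib and 50/30/20/0% for pooled bDMARD, with hazard multiplied by g per line. Spurious HR = (0.1 + 0.2g + 0.3g² + 0.4g³) / (0.5 + 0.3g + 0.2g²).

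- g = 1.1: 1.215/1.072 = 1.13
- g = 1.2: 1.463/1.148 = 1.27
- g = 1.3: 1.746/1.228 = 1.42

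*3+ patients left out of the aggregate.* Take 500 tofacitinib and 5050 bDMARD patients, 10/1000 PY, HR 2, five years of uniform accrual, 5% annual loss in the tofacitinib arm and two-sided 0.05. Expected bDMARD events are 5050 × [1 − (1 − e^−0.05)/0.05] = 124, and expected tofacitinib events are 22.3. Power = Φ(ln 2/√(1/d₁ + 1/d₀) − 1.96), where d₁ and d₀ are tofacitinib and bDMARD events.

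| Assumed 3+ share dropped | Tofacitinib events | Power |
|---|---|---|
| 0% | 22.3 | 0.85 |
| 20% | 17.8 | 0.78 |
| 40% | 13.4 | 0.67 |
| 60% | 8.9 | 0.52 |

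The protocol's Table 2 gives 0.73 for the base cell, so only the relative loss can be read from these rows. Table 2 itself shows what halving 500 tofacitinib patients to 250 costs with about 11,100 bDMARD patients: 0.75 to 0.38 for malignancy and 0.47 to 0.20 for MACE.

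*VTE factor left out.* With an assumed rate ratio of 3 and prevalence of 10% (tofacitinib) versus 20% (bDMARD), the HR is multiplied by (1 + 0.10 × 2)/(1 + 0.20 × 2) = 1.2/1.4 = 0.86. With the prevalences reversed, the factor is 1.4/1.2 = 1.17.

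**The case against.** The strongest answer is that Appendix 2 calls its shells a general outline, and that Section 9.7.2 leaves the confounders to an SAP and allows propensity matching or weighting. That stands against the inference that the covariates are locked: they are set out, not fixed. It does not remove the mismatch, because the same section ties the reports to these shells, and the shells spell out named models rather than staying silent.

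Other stronger readings also fail:

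- *Line of therapy is ignored.* It is not. Table IV stratifies by it up to two prior biologics. Table III's rows are blank in the text at hand. If its comparators are the line-specific cohorts, line is partly handled, though tofacitinib would still be pooled over all lines.
- *Patients with 3+ prior biologics are lost to the study.* They have a rate row in Table II, and nothing excludes them from Table III. Leaving them out of Table IV could even fit the overlap requirement in Section 9.7.2; the gap is that this is not stated.
- *The CV and VTE factors are left out as a group.* Age, MI, diabetes and cancer are in HRb to HRd.
- *Label changes have made the cohorts differ.* The protocol reports changes to the SmPC, not to prescribing. It stratifies HRs by start year and, if feasible, splits incidence rates at 31 January 2020 and June 2021. The start-year strata do not remove imbalance within a year, and the splits concern rates, not HRs.
- *Complete-case and missing-indicator handling of DAS28 and HAQ is a defect.* The shells show both side by side, no missingness figure is given, and the choice of method belongs in an SAP. No point is made of it here.

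**Conclusion.** The concern holds as an inconsistency within the protocol that should be corrected before any comparative analysis. Prior-biologic count is in none of the four models. Table IV covers three of four lines and leaves the 3+ patients without a comparator or a stated role in the aggregate. Nine of the 15 distinct CV and VTE risk factors never reach a hazard ratio.

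A reader might take the illustrated spurious HRs of 1.13 to 1.42, the power losses or the factor of 0.86 as findings. The documents do not support that: line mix, hazard gradient, 3+ share and risk-factor prevalence are all assumed, and the VTE bias could run either way. The figures show only that plausible inputs would matter. The conclusion also assumes that the shells would be populated as written; an SAP not shown here may already have changed them.

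**What to change.** - **3+ stratum.** Add a fourth-or-later bDMARD starter comparator to Tables I and II and a 3+ row to Table IV. Include it in the aggregate where overlap and the shells' five-event rule allow. Otherwise state that the aggregate excludes 3+ patients. The size of such a cohort is not known from the protocol.
- **Treatment history.** Add number of prior b/tsDMARDs to the Table III models where tofacitinib is compared with pooled bDMARD initiators. Do not add it for the naive or general population comparisons, where it has no meaning. Against a single-line cohort it is constant in the comparator and would only extrapolate.
- **Outcome-specific covariates.** For MACE and MI add the Section 9.3.1 CV factors, and for VTE the VTE factors. Use a propensity score where events are few; Section 9.7.2 already allows propensity methods.

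The cost is edits to the shells and the SAP, since the variables are already planned for collection. The downside is more covariates for rare outcomes, which the score is meant to contain.

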#### **9.2.1.3. ts/bDMARD-naïve RA Cohort**

- At least two separate visits documented in Swedish Patient Register listing RA as a diagnosis code for the visit, with at least one visit at a unit of Rheumatology or Internal Medicine.
- Patients are censored from this cohort when they start tofacitinib or a bDMARD, but are eligible for subsequent inclusion into the respective drug-based cohorts defined above.
- To ensure a contemporaneous cohort, diagnosis of RA must have occurred after 01 January 2012.

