#### **9.2.1.4. General Population Cohort**

- Randomly selected from general population and region-, age- and gender-matched to RA patient cohorts, up to 5 population controls per tofacitinib exposed patient.

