#### **9.4. Data Sources**

##### **9.4.1. SRQ**

SRQ is the source of disease activity information, measured by C-reactive protein (CRP), erythrocyte sedimentation rate (ESR), health assessment questionnaire (HAQ), number of swollen and tender joints, and patient's global assessment of disease (on a visual analog scale(VAS)) and doctor's evaluation on a Likert type scale. In addition, disease activity scores -28 (DAS 28), the European League Against Rheumatism (EULAR) response criteria, and the American College of Rheumatology criterion of improvement (ACR) can be calculated. Reflecting the changes in treatment paradigm, Table 1 shows how the disease activity in RA at the time of first biologic start has decreased over time. Although the system

was originally developed for RA, clinical variables of importance for specific rheumatic diseases have been added incrementally.

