#### **9.4.3. The Patient Register and the Prescribed Drug Register**

The Swedish Patient Register provides information on all hospitalized (inpatient treated) patients, and all visits to non-primary outpatient care (such as a visit to a rheumatologist). Diagnoses are assigned by the discharging physician, as well as date of discharge, discharging hospital and department. Diagnoses are coded according to the International Classification of Diseases (ICD), with version 8 used until 1986, version 9 1987 to 1996 and version 10 (ICD10) since 1997.

In addition to data on safety outcomes and baseline comorbidities or disease history, the patient register is the source of comparator cohorts defined by diagnosis, but untreated with biologic agents.

The Prescribed Drug Register provides all retrievals of prescribed drugs in Sweden from July 2005, and may be used to aid correct classification of patients by their history of retrieved DMARDs, or to define subcohorts based on switches in treatment.

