### **9.9. Limitations of the Research Methods**

This study is designed to monitor the safety of tofacitinib within the clinical practice setting utilizing the ARTIS Register, a well-established Swedish-based rheumatology register. Despite the strengths of the register, data must be evaluated in light of their limitations. For example, consistent with most observational studies, the possibility of channeling and endpoint misclassification, are of concern in interpreting findings.

As a new therapy in the RA treatment armamentarium, it is possible that patients treated with tofacitinib will represent those with the most severe cases of disease, longer disease duration,

history of multiple failed RA therapies and physical comorbidities that place patients at risk for events. Biases resulting from channeling may present as increased rates of safety events of interest in the early phases of the study. Comparison to internal comparators may illuminate such channeling. Stratification on key indicators of disease severity, patient characteristics and past therapies can be done for contextualization. Trend analyses may be conducted to evaluate rates in tofacitinib patients over time.

The RA treatment landscape has evolved over time with the introduction of new therapies, treatment recommendations, and approaches to patient management. The rates of safety events of interest and their distribution among patient-types may have changed over time. The comparators in this study are not exclusively contemporaneous to tofacitinib treated patients. Analysis may be unable to identify or control for any changes in rates due to changes in the treatment landscape.

Event misclassification is of particular concern within the observational setting due to less stringent monitoring relative to clinical trials. While ARTIS has an established system to identify and capture endpoint data, all events cannot be fully verified via source documentation. Instead, linkage to national health care registers allows the register to obtain data on all safety events of interest (regardless of suspected causal relationship to the treatments), and on comparator cohorts, so that any potential risk increases can be evaluated in light of risks among patients and with other treatments, and the general Swedish population.

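### The severity-adjusted models in Table III (HRc, HRd) are not limited to cohorts with SRQ data, and HRd's missing indicator leaves severity confounding roughly in proportion to the share of missing values

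*Protocol*

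**What the plan says.** Protocol Appendix 2, Table III, is titled "Results from adjusted Cox regressions comparing tofacitinib initiators to comparator cohorts for each outcome". Its notes build four models:

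- HRa and HRb adjust for age, sex, inpatient days and comorbidity history. Neither contains DAS28 or HAQ.
- HRc adds "Rheumatoid factor, HAQ(linear), RA disease duration, DAS28(linear), DMARDs, steroids. Complete case analysis".
- HRd is "as HRc but using a missing indicator, and quartiles, for HAQ and DAS28".

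On where the data come from:

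- Section 9.4.1: "SRQ is the source of disease activity information".
- Section 9.2.1.3 defines the naïve cohort by "At least two separate visits documented in Swedish Patient Register listing RA as a diagnosis code for the visit", and Section 9.4.3 adds that "the patient register is the source of comparator cohorts defined by diagnosis, but untreated with biologic agents".
- Section 9.2.1.4 describes the general population cohort as "Randomly selected from general population and region-, age- and gender-matched to RA patient cohorts".

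Section 9.7.2 says the reports will contain populated tables in line with the Appendix 2 shells. Section 9.9 warns of channeling: "it is possible that patients treated with tofacitinib will represent those with the most severe cases of disease". In Annex 2, the checklist item on handling missing data (10.7) is ticked as not applicable, although the Table III notes do state a method.

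**The concern.** There are two separate problems.

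**Scope.** Table I in the same appendix lists biologics-naïve patients and the general population among the comparator cohorts. Section 8 plans severity-adjusted Cox regressions against the other comparator cohorts. Table IV is confined to bDMARDs; Table III is not. Read as written, the two models are also run where their covariates do not exist.

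**Method.** Within bDMARD comparisons, complete-case analysis discards events when the protocol already expects tofacitinib uptake to limit power (Section 9.5). A missing indicator keeps the patients but does not adjust for severity among those with missing values. If tofacitinib does go to sicker patients, what is left pushes the HR above 1, which in a safety study can look like a drug effect.

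**Working it through.** The protocol states no missing share and no power for HRc or HRd, so there is no figure of its own to reproduce. Missing shares of 10% to 50% are assumed below.

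**1. General population comparator.** Let X = 1 for tofacitinib and M = 1 if severity is missing. Every comparator has M = 1.

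- HRc keeps only M = 0, which leaves 0 comparator patients.
- HRd with complete tofacitinib data has M = 1 − X exactly, so the indicator and the exposure are collinear (design rank 4 of 5) and no HR can be estimated.
- HRd with some missing tofacitinib data can compare the cohorts directly only where M = 1. One simulated data set per setting (500 tofacitinib, 2,500 comparators, one severity variable) gave:

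| Missing in tofacitinib | Tofacitinib events with M = 1 | SE of log HR, HRd | SE, no severity term |
|---|---|---|---|
| 5% | 1 of 57 | 1.00 | 0.15 |
| 20% | 8 of 54 | 0.36 | 0.15 |
| 30% | 18 of 46 | 0.24 | 0.16 |

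HRd's indicator covers only HAQ and DAS28. Rheumatoid factor and RA duration come over from HRc, whose rule is complete cases. Read literally, HRd then also has no general-population comparators.

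**2. HRd against bDMARD initiators.** Under random missingness, the estimate is roughly a mix of an adjusted HR (values present) and a severity-unadjusted HR (values missing). The confounding left should therefore be close to the missing share. A Cox simulation checks this. Assumptions: true HR 1, tofacitinib 0.5 SD more severe, log-HR 0.4 per SD, values missing at random within cohort.

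Share left = [ln(HRd) − ln(Q)] / [ln(crude) − ln(Q)], where Q is the same quartile model with no values missing.

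| Missing, both cohorts | Crude | Q | HRd | Share left | HRc |
|---|---|---|---|---|---|
| 10% | 1.228 | 1.045 | 1.062 | 0.016/0.161 = 10% | 0.990 |
| 20% | 1.173 | 1.005 | 1.032 | 0.027/0.155 = 17% | 0.992 |
| 30% | 1.198 | 1.015 | 1.067 | 0.050/0.166 = 30% | 0.993 |
| 50% | 1.236 | 1.042 | 1.142 | 0.092/0.171 = 54% | 1.025 |

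With 20% missing in tofacitinib and 80% in the comparator, the share left is ln(1.161/1.071)/ln(1.257/1.071) = 0.081/0.160, about 50%. Simulation noise is visible: the full-data linear model, whose true value is 1, ranged from 0.973 to 1.010 across the four rows. Only the comparison of HRd with Q within a row should be read.

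The size depends on the assumed severity effect. A separate null simulation at 30% missing gave HRd-type values of 1.05 to 1.11 (0.5 SD gap, log-HR 0.3 to 0.5; crude 1.15 to 1.27). With a 1 SD gap and log-HR 0.5 it gave 1.25 (crude 1.62).

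**3. Precision cost of HRc.** If a share m is missing, intervals widen by 1/√(1 − m): 1.05, 1.12, 1.20 and 1.41 at 10%, 20%, 30% and 50%.

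For scale, take 500 tofacitinib and 5,050 bDMARD patients at 10/1000 PY. Table 2 states power 0.73 for this cell. An exact conditional test gives 0.71 with 5-year uniform accrual and 5% annual tofacitinib loss; no method tried reproduces all of Table 2. The Schoenfeld formula is power = Φ(√[D·p(1 − p)]·ln 2 − 1.96), with p = 500/5550 = 0.090.

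- No missing values: D = 22.3 + 124.2 = 146.5, so √(146.5 × 0.0820) × 0.693 − 1.96 = 0.44 and power is 0.67.
- 30% missing: D = 102.5, which gives 0.05 and power 0.52. The exact test falls from 0.71 to 0.59.

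For the 344 patients projected in Section 9.5 (entry over 24 months, 5 to 7 years of follow-up, 5% annual loss), malignancies at 10/1000 PY number 344 × 5.18 × 0.01 = 17.8. At 30% missing that falls to 12.5.

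**The case against.** The best defence is that Appendix 2 calls the shells a general outline and that the SAP, not shown here, governs the final adjusted analyses. Section 9.7.2 also allows propensity score matching or inverse probability weighting, and Table IV stratifies by number of previous biologics, so HRc and HRd are not the only handle on channeling. No model is named as the main one, and HRc and HRd side by side can be seen as a paired check. This lowers the stakes but does not remove the point. Section 9.7.2 ties the reports to these shells, the notes do state a missing-data method, and propensity methods also need a rule for missing DAS28 and HAQ.

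On scope, the comparator rows of Table III are blank, so running HRc and HRd against the general population is implied, not stated. The rule of at least 5 events in both cohorts would stop HRc there, if it is applied after incomplete cases are dropped. Both are fair, and both show that the note needs a sentence.

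Three stronger readings are tempting and are not supported:

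- **That HRd leaves the channeling bias in place, so a false tofacitinib excess is to be expected.** HRd still adjusts patients with recorded values. At 10% to 20% missing it differs from the same model without missing data by about 0.02 to 0.03 in the HR. Section 9.9 calls channeling of severe patients possible, not established.
- **That HRc is biased.** It stayed at 0.99 to 1.03 in the simulation with equal missingness. Complete-case regression also remains valid when missingness depends on the covariates, even on unseen severity, provided it does not depend on outcome given covariates. Imputation under missing at random can fail in that case.
- **That neither model works for any cohort outside SRQ.** This is clear only for the general population. Section 9.2 says SRQ initially focused on early RA and later widened, so some naïve patients may have DAS28 and HAQ. The share is not given.

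**Conclusion.** The point holds in a limited form. As the notes stand, HRc and HRd cannot give a usable severity-adjusted comparison with the general population, and their use for the naïve cohort depends on an SRQ coverage that the protocol does not state. The general-population result follows from the data sources and needs no assumption about effect sizes.

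Against bDMARD initiators, HRd leaves about 10% to 54% of the severity confounding on the log-HR scale at 10% to 50% missing. This is minor at the low end and material at the high end. It rests on an assumed severity gap, an assumed severity effect, one severity variable and random missingness within cohort. HRc's demonstrated cost is precision, with intervals about 20% wider at 30% missing. A reader might infer that the final analysis will be wrong; the documents do not show that, since the SAP may refine the shells. The weakness is in what the shell fixes, and it should be corrected before comparative reports are produced.

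**What to change.** In the Table III notes, and in the SAP to match:

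1. Limit HRc and the model that replaces HRd to bDMARD comparisons. Stop at HRa and HRb for the general population, and for the naïve cohort unless its SRQ coverage is shown to be adequate.
2. Report the share of missing DAS28, HAQ, rheumatoid factor and disease duration by cohort.
3. Replace the missing-indicator model by multiple imputation of those four covariates. Put cohort, all covariates, the event indicator and the cumulative baseline hazard in the imputation model, and keep DAS28 and HAQ continuous.
4. Keep complete-case HRc beside it, because the two rest on different missingness assumptions and agreement between them is informative.
5. Carry the new definition to Table IV, which has an HRd column but no HRd note, and correct checklist item 10.7.

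The cost is table-note and SAP wording plus some extra programming. The downside is that the imputed model relies on missing at random, which is why HRc stays.
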